6.0 SAFETY MONITORING AND ADVERSE EXPERIENCE REPORTING

6.1 Safety Monitoring

Close cooperation between the study team members will be necessary in order to monitor participant safety and respond to occurrences of toxicity in a timely manner. The team will meet via conference call every two weeks during the period of study implementation, and additional ad hoc calls will be convened if required.

The study site Investigators are responsible for continuous close monitoring of all AEs that occur among study participants, and for alerting the rest of the protocol team if unexpected concerns arise. In particular, Investigators will immediately report to the protocol team the occurrence of any grade 3 or higher AE (as defined by the DAIDS Toxicity Tables) judged possibly, probably, or definitely related to product use.

Accrual will be suspended if two or more participants in any cohort experience a grade 3 or higher AE judged possibly, probably, or definitely related to product use. An independent statistician then will review all data pertinent to these AEs – including the participants' random assignments. If the participants who experienced the AEs were assigned to different study products, the statistician will recommend to the study team that the study continue (without providing any further information that would unblind the team). If the participants who experienced the AEs were assigned to the same study product, the study team will be unblinded and the following actions will be undertaken:

- If the participants who experienced the AEs were assigned to the control gel, the protocol will be amended to eliminate application of the control gel.
- If the participants who experienced the AEs were assigned to CS gel, the study team will review all available safety data and determine whether to allow the study to proceed. A decision to stop the study may be made at this time or at any such time that the team agrees that an un acceptable type and/or frequency of AEs has been observed.

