7.2 Endpoints

7.2.1 Primary Endpoints

Consistent with the primary study objectives to assess the local and systemic toxicity of 6% CS gel versus the control gel on the vulvar and cervicovaginal mucosa of HIV-infected women, the following endpoints will be assessed among female study participants:

- Genital symptoms judged by the Investigator to be possibly, probably, or definitely related to product use.
- Pelvic exam findings, including colposcopic findings, judged by the Investigator to be possibly, probably, or definitely related to product use.
- Grade 3 or higher laboratory values (as defined by the DAIDS Toxicity Tables) observed among female participants for hematology, liver or renal function, and coagulation judged by the Investigator to be possibly, probably, or definitely related to product use;
- Adverse experiences judged by the Investigator to be possibly, probably, or definitely related to product use.

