7.5 Blinding

Throughout the period of study implementation and data analysis, neither study staff nor participants will be informed of the participants' random assignments (except as specified in section 6.1). Both study products will be supplied in identical, single-use applicators packaged in individual white wrappers. Study staff and participants will be unblinded after all study visits and data analyses are completed. Individual exceptions may be considered by the Protocol Chair and Medical Officer in situations where product information may be needed to protect the safety of the participant. In emergency situations, if a participant experiences an SAE that, in the opinion of the Investigator requires immediate unblinding, the study site pharmacist may disclose the treatment assignment to the Investigator without obtaining prior concurrence of the Protocol Chair and Medical Officer.

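### Section 6.1 unblinds the study team without limit when the triggering events share a gel, so investigators who judge the primary endpoints may continue unblinded if the study proceeds after a CS gel signal

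*Protocol*

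**What the plan says.** Section 6.1 sets the trigger in terms of events attributed to the gel: "Accrual will be suspended if two or more participants in any cohort experience a grade 3 or higher AE judged possibly, probably, or definitely related". The next step is kept away from the team: "An independent statistician then will review all data pertinent to these AEs", including the random assignments.

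Three outcomes follow.

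- **Different gels.** The statistician recommends that the study continue, "without providing any further information that would unblind the team".
- **Same gel, control.** The team is unblinded and "the protocol will be amended to eliminate application of the control gel".
- **Same gel, CS.** The team is unblinded, and "the study team will review all available safety data and determine whether to allow the study to proceed".

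The sentence behind the last two outcomes is "If the participants who experienced the AEs were assigned to the same study product, the study team will be unblinded". It names no role to be left out. It does not say whether the team learns the assignments of the affected women, of the cohort, or of everyone.

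Section 7.5 treats this as an exception to the general blind: "neither study staff nor participants will be informed of the participants' random assignments (except as specified in section 6.1"). Section 7.2.1 lists four primary endpoints, each of which counts only what the Investigator judges related to product. One of them is "Pelvic exam findings, including colposcopic findings, judged by the Investigator to be possibly, probably, or definitely related to product use".

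**The concern.** The person who decides whether a symptom, examination finding, laboratory value or AE counts as a primary endpoint should not know the gel. Section 6.1 can remove that protection just after a possible CS gel signal, when unbiased later observations matter most. An Investigator who knows that a woman is on CS gel, and that two serious events have been attributed to it, may call a doubtful finding related more readily than in a control woman. The same judgement feeds the Section 6.1 trigger, so later safety reviews could be affected as well.

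The protocol does not need this step in order to reach a decision. The independent statistician already holds the codes, and the different-gel outcome shows that the authors meant to protect the team's blind where they could.

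**Working it through.** **Step 1. Who is unblinded.** The protocol text does not define the study team. Section 6.1 makes site Investigators responsible for alerting the rest of the protocol team, which counts them as members. The exception in Section 7.5 qualifies a rule about study staff, not about a committee. Nothing in the text contradicts this reading, but it remains an inference.

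**Step 2. Whose judgement is exposed.** All four endpoints in Section 7.2.1 depend on the Investigator's view of relatedness. No section provides a separate blinded assessor.

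**Step 3. Who is still to be assessed.** Suspending accrual does not end follow-up. Women already enrolled still have Day 7 and Day 14 examinations (Sections 5.4 and 5.5). Later cohorts follow in sequence if the study proceeds (Section 2.4.3).

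**Step 4. Check on the plan's own figures.** The protocol gives no figure for the unblinding rule. The nearest is the Section 7.3 table, which states 0.12 for two or more events among 12 women at a 5% rate. The exact binomial gives 1 − 0.95¹² − 12 × 0.05 × 0.95¹¹ = 1 − 0.540 − 0.341 = 0.118, which agrees.

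**Step 5. How often a trigger leads to the CS branch.** Assume equal risk on both gels, two events, and m women per gel. The sizes come from the letter of amendment of 1 August 2003: m = 12, 12, 6 and 10. Given the first event, the second falls on the same gel with probability (m − 1)/(2m − 1). Half of these cases are on CS gel.

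| Cohort | m | Same gel | CS gel (half) |
|---|---|---|---|
| 1 and 2 | 12 | 11/23 = 0.478 | 0.239 |
| 3 | 6 | 5/11 = 0.455 | 0.227 |
| 4 | 10 | 9/19 = 0.474 | 0.237 |

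The CS column is the relevant one. On the control branch the control gel is dropped, so later assessment is open whatever the blinding rule says.

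**Step 6. How often the branch would be reached at all.** This needs the rate of related grade 3 or higher AEs, which the protocol does not give. The rates below are assumptions, equal on both gels. For each cohort, the chance of the CS branch is P(two or more events among 2m women) × the CS fraction from Step 5, counting the first two events only. At 5% in a 24-woman cohort, P(two or more) = 1 − 0.95²⁴ − 24 × 0.05 × 0.95²³ = 1 − 0.292 − 0.369 = 0.339, and 0.339 × 0.239 = 0.081. The last column is one minus the product of (1 − chance) over the four cohorts, taking all four as run.

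| Assumed rate | Cohort 1 or 2 | Cohort 3 | Cohort 4 | At least one cohort |
|---|---|---|---|---|
| 1% | 0.006 | 0.001 | 0.004 | 0.017 |
| 2% | 0.020 | 0.005 | 0.014 | 0.058 |
| 5% | 0.081 | 0.027 | 0.063 | 0.230 |
| 10% | 0.169 | 0.078 | 0.144 | 0.455 |

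The branch can therefore be reached with no difference between the gels. It is uncommon at low rates and common at high ones.

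**Step 7. Narrow disclosure can still leak.** Cohorts 1 and 2 target three women per gel among six at each site. If both affected women were at one site and on CS gel, the other four would be one on CS gel and three on control. An Investigator told only two assignments could guess the rest. Who is told therefore matters as much as what is told.

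**The case against.** The strongest case for the protocol is that this is a disclosed choice, cross-referenced in Section 7.5, for a small Phase I study in which clinicians who know the cases review a same-gel signal. The clause contradicts no other section and misstates no figure.

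Three stronger readings are tempting, and the documents do not support them.

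- **All later women would be assessed unblinded.** A reader might infer that a trigger in Cohort 1 exposes all 24 + 12 + 20 = 56 of the 80 women in Cohorts 2 to 4. That needs the widest reading of an unstated scope. The statistician reviews data pertinent to the triggering events. Later assignments come from sealed envelopes, and the site pharmacist uses the code list (Section 7.4). Section 5.8 gives Investigators each participant's assignment only after the analyses. The figure of 56 is a worst case.
- **About half of triggers cause the harm.** The 45% to 48% for same-gel events counts both gels. A change in who is unblinded helps only on the CS branch, about half of that.
- **The double-blind comparison is lost.** Judgements made before the trigger stand. Section 7.6.1 also tabulates AEs overall and by severity and summarises laboratory measures, and colposcopic images are taken. The blind is imperfect in any case, since Sections 4.1.1 and 4.1.2 describe gels that differ in appearance and viscosity.

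It is also fair to say that no section places colposcopists or interviewers in the deciding group, and that the Protocol Chair might examine participants. Blinded Investigators might still work out that a signal was on CS gel, because the other two outcomes look different from outside.

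These points limit the size of the problem and shape the remedy. They do not supply the missing limit on roles and scope in Section 6.1.

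**Conclusion.** The point holds in a limited form. As written, Section 6.1 allows the Investigators whose judgement defines the primary endpoints to be unblinded and then to go on assessing women if the study proceeds after a CS gel signal. For women whose assignments are disclosed and who are still in follow-up, this follows from the text once Investigators count as part of the team. For later enrolees it depends on a scope that the protocol leaves open.

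At equal risk and with two events, the CS branch follows 24% of triggers in Cohorts 1 and 2, 23% in Cohort 3 and 24% in Cohort 4. The absolute chance cannot be stated, because the event rate is not given. Under the assumed rates of 1% to 10% it runs from about 0.02 to 0.455 over the four cohorts. The conclusion rests on the inferred membership of the team. The right label is a cheap improvement rather than a defect that invalidates the design.

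**What to change.** Amend Sections 6.1 and 7.5 as follows.

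- When the triggering events share a gel, the independent statistician discloses only the assignments of the affected women, together with aggregate safety tables by gel.
- Disclosure goes only to designated decision-makers who do not assess endpoints. The Protocol Chair and Medical Officer are natural candidates, since Section 7.5 already gives them a role in unblinding. If either examines participants, a non-assessing member of the existing team takes that place.
- If the study proceeds, site investigators and examiners stay blinded to individual assignments.
- Emergency unblinding in Section 7.5 is unchanged, as are the trigger, the suspension of accrual and the safety review.

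The cost is wording, with no new staff. The downside is that site investigators contribute to the safety decision on blinded data only, and they may still infer that the signal was on CS gel. The change does not help on the control branch, where dropping the control gel makes later assessment open.

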7.6.1 Primary Analyses

The primary aims of the study are to assess the local and systemic toxicity of once and twice daily application of 6% CS gel versus a control gel among HIV-infected women. The control gel provides information regarding signs, symptoms and/or morbidity that may be attributed to normal variation and/or the study procedures or use of applicator rather than the investigational product being studied. Primary data analyses will tabulate the number of primary endpoints — listed in Section 7.2.1 — observed during the study, by study cohort and product assignment within cohorts. All participants who enroll in the study will be included in each tabulation. Individual participants will contribute once to the calculation of event rates.

Additional safety analyses will tabulate the number and type of AEs observed overall and by severity and relationship to product, by cohort and product assignment. AEs that lead to discontinuation of product use and/or study participation will be tabulated separately. The temporal relationship of product application and AE onset, and the duration of symptoms, also will be evaluated. Finally, baseline, Day 7, and Day 14 laboratory measures will be summarized and the change in function, defined as the difference between the baseline and Day 14 measurements, will be described.

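### Section 6.1 drops the control gel after two related grade 3+ control-gel AEs without the all-data review it requires for CS gel, and sets no limit on unblinding of the study team (minor)

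*Protocol*

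**What the plan says.** The trigger in section 6.1 is counted within a cohort and covers only events with at least a possible link to the product: "Accrual will be suspended if two or more participants in any cohort experience a grade 3 or higher AE". The steps that follow are:

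- "An independent statistician then will review all data pertinent to these AEs", with the random assignments in hand.
- If the women used different products, the statistician recommends continuing and the team stays blinded.
- If they were "assigned to the same study product, the study team will be unblinded".
- Both on control gel: "the protocol will be amended to eliminate application of the control gel".
- Both on CS gel: "the study team will review all available safety data and determine whether to allow the study to proceed".

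Section 2.4.3 announces a safety data review after two such events but refers to 6.1 for how it is done. Section 7.5 exempts 6.1 from the blinding rule. Section 10.4 requires the Protocol Chair, the NIAID Medical Officer, the IRBs and the DAIDS regulatory office to approve any amendment. Neither letter of amendment changes 6.1. The letter of 1 August 2003 sets the cohorts at 24, 24, 12 and 20 women, half on each gel.

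**The concern.** The two same-product branches are treated differently. A CS-gel pair leads to a review of everything and then a decision. A control-gel pair leads to a prescribed outcome after a review tied to the triggering events. Because the trigger is counted within one cohort, nothing in the control branch requires anyone to look at related AEs on CS gel in completed cohorts before the comparator goes.

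Section 7.6.1 explains why that comparator is there: "The control gel provides information regarding signs, symptoms and/or morbidity that may be attributed to normal variation", or to study procedures or the applicator. Two control-gel events could be exactly that background. Removing the gel ends concurrent measurement of it, and the local-toxicity objective in section 2.1, framed against a control gel, could not be met as designed for women enrolled afterwards.

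The second issue is unblinding. Section 6.1 does not say which team members are told, or whether they learn all assignments or only those of the affected women. It makes site Investigators responsible for "alerting the rest of the protocol team if unexpected concerns arise", which suggests that they belong to the team. Their relatedness judgement enters all four primary endpoints in section 7.2.1, for example "Adverse experiences judged by the Investigator to be possibly, probably, or definitely related to product use". If a CS-gel pair occurs and both gels continue, later judgements could be made by people who know the product.

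**Working it through.** **Plan's own figures first.** Section 7.3, as amended, gives the chance of two or more events among 12 women at a 5% rate as 0.12. The exact binomial gives 0.118. The other rows for 12 women, and the tables for 6 and 10 women, also reproduce.

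**Inputs.** Amended cohort sizes are n = 24, 24, 12, 20, with m = n/2 per gel. The protocol gives no rate of related grade 3+ AEs, so equal rates of p = 1% and 2% per woman in both gels are assumed. Cohorts are treated as independent.

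**Step 1: share of triggering pairs that are all-control.** With equal rates, the chance that the first two events in a cohort are both on control is m(m-1)/(n(n-1)):

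- n = 24: 12×11/(24×23) = 0.239
- n = 12: 6×5/(12×11) = 0.227
- n = 20: 10×9/(20×19) = 0.237

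**Step 2: control trigger per cohort.** t = P(2 or more events among n women) × that share.

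| p | P(≥2) in Cohorts 1, 2, 3, 4 | t in Cohorts 1, 2, 3, 4 |
|---|---|---|
| 1% | 0.0239, 0.0239, 0.0062, 0.0169 | 0.0057, 0.0057, 0.0014, 0.0040 |
| 2% | 0.0826, 0.0826, 0.0231, 0.0599 | 0.0198, 0.0198, 0.0053, 0.0142 |

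**Step 3: over the four cohorts.**

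- Any control-gel trigger, 1 − Π(1 − t): 0.0167 at 1%, 0.0577 at 2%.
- Any same-product pair, and so unblinding of the team, 1 − Π(1 − 2t): 0.0332 at 1%, 0.1131 at 2%.

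**Step 4: control women lost.** The plan has 12 + 12 + 6 + 10 = 40 control women. A first control trigger in Cohort 1, 2, 3 or 4 removes 28 (12+6+10), 16 (6+10), 10 or 0 later control women, plus any not yet enrolled in that cohort. Averaged over all trials, with or without a trigger, the loss of later control women is 0.26 at 1% and 0.91 at 2%.

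**Step 5: what the all-data review might find.** If the first two events in a cohort are both on control, no woman on CS gel in that cohort has yet had a related grade 3+ AE, so any such event lies in an earlier cohort. Before Cohorts 2, 3 and 4 there are k = 12, 24 and 30 CS-gel women. The chance of at least one event among them is 1 − (1−p)^k: 0.114, 0.214, 0.260 at 1%, and 0.215, 0.384, 0.455 at 2%. The joint chance with a control trigger is:

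- 1%: 0.0057×0.114 + 0.0014×0.214 + 0.0040×0.260 ≈ 0.002
- 2%: 0.0198×0.215 + 0.0053×0.384 + 0.0142×0.455 ≈ 0.013

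This sum ignores stopping in earlier cohorts, which would lower it slightly. It counts only related grade 3+ events; a review of all safety data would also cover milder and unrelated ones.

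**Sensitivity.** At 5%, the rate that section 7.3 uses as its worked example for an unspecified endpoint, step 3 gives 0.230 and 0.419 and step 5 about 0.105. The protocol does not offer 5% as a rate of related grade 3+ AEs, so these figures are only an upper illustration.

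**The case against.** The strongest defence is that the asymmetry is sensible. CS gel is the product under study, so stopping it needs weighing. The control is a marketed lubricant given only as a reference, and two related grade 3+ events on it are good reason to withdraw it. CS-gel events in earlier cohorts would not make the control gel safer. This stands as far as the outcome goes: dropping the control may be right. It does not explain why the full data need not be reviewed first.

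A second defence is that safeguards already exist. The team confers every two weeks, Investigators report related grade 3+ AEs at once, and removal needs an approved amendment. The team may well know of earlier events, though without assignments until it is unblinded. None of these provisions requires a review of all safety data before the control is removed. The amendment route does mean that the extra review need add no delay.

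Third, the text does not rule out a substitute comparator, so the losses of 28, 16 and 10 later control women assume that none is introduced. Completed cohorts keep their blinded comparison.

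Fourth, unblinding is deliberate, since section 7.5 exempts it, and it ceases to matter once only one gel is in use. Both points are correct. What remains is a CS-gel pair followed by a decision to continue with both gels.

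A reader might infer more than the documents support:

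- That the control gel goes without any review. The statistician does review the data pertinent to the triggering AEs.
- That sections 2.4.3 and 6.1 conflict. Section 2.4.3 defers to 6.1.
- That site Investigators will certainly learn every assignment. Their inclusion is inferred from the references to the study team and the protocol team, and the scope of unblinding is not stated.

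**Conclusion.** The point holds as a minor design weakness. Section 6.1 prescribes loss of the comparator in one branch without the all-data review that it requires in the other, and leaves the extent of unblinding open in both.

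Under equal rates of 1% and 2%, the control branch fires in 1.7% and 5.8% of trials, and any same-product pair occurs in 3.3% and 11.3%. The control branch coincides with an earlier related grade 3+ AE on CS gel in about 0.2% and 1.3%. The chances of 11% to 45% in step 5 apply only once a control trigger has occurred in Cohort 2, 3 or 4; they do not describe the trial as a whole.

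The minor grading rests on such AEs being rare, which is an assumption because the documents give no rate. The 23-24% all-control share depends on equal rates and 1:1 allocation, and hardly at all on the level of the rate.

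**What to change.** Amend section 6.1 by letter of amendment:

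1. In either same-product case, require a review of all available safety data, from completed cohorts as well as the current one, before an arm is changed. Keep elimination of the control gel as one possible outcome.
2. Limit unblinding to the independent statistician and named decision makers, for example the Protocol Chair and Medical Officer. State which assignments they see, and keep site Investigators blinded while both gels remain in use.

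This is a cheap improvement that needs no new participants, staff or procedures. It costs one review meeting while accrual is already suspended, and fewer team members see unblinded data when the decision is made.

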6.2 Adverse Experience Reporting Requirements

An AE is defined as any untoward medical occurrence in a clinical research participant administered an investigational product and which does not necessarily have a causal relationship with the investigational product. As such, an AE can be an unfavorable or unintended sign (including an abnormal laboratory finding, for example), symptom or disease temporally associated with the use of an investigational product, whether or not considered related to the product.

Study participants will be provided a 24-hour telephone number and instructed to contact the study clinician to report any AEs they may experience, except for life-threatening events, for which they will be instructed to seek immediate emergency care. Where feasible and medically appropriate, participants will be encouraged to seek medical care where the study clinician is based, and to request that the clinician be paged or otherwise contacted upon their arrival. With appropriate permission of the participant, records from all non-study medical providers related to AEs will be obtained and required data elements will be recorded on study case report forms. All participants reporting an AE will be followed clinically, until the AE resolves (returns to baseline) or stabilizes.

Site staff also will report all AEs that meet SAE reporting requirements according to the procedures set forth in the Study-Specific Procedures Manual and the time frames set forth in the DAIDS SAE Reporting Manual. Specifically, DAIDS-defined "intensive" reporting requirements will be followed for this study.

Active follow-up for safety outcomes (serious and non-serious AEs) in each study participant will end one day after the final application of study product, however all SAEs reported by participants during the study treatment period and/or during the eight-week period following the final application will be reported in accordance with the DAIDS manual. Information on all AEs will be included in reports to the US Food and Drug Administration (FDA), and other applicable government and regulatory authorities. Site staff will report information on all AEs and SAEs to their Institutional Review Board (IRB) in accordance with all applicable regulations and local IRB requirements.

Note: The above-stated reporting requirements apply to enrolled female study participants. Participants and their male sexual partners will be instructed to report AEs experienced by male partners to the study clinician, who will evaluate and document the experience, as well as provide follow-up care or a referral for such care. In the event that a male partner experiences an AE that meets SAE reporting requirements, the experience will reported as an SAE according to the procedures set forth in the Study-Specific Procedures Manual and the time frames set forth in the DAIDS SAE Reporting Manual.

